participant. This role will be referred to as ‘mixer’. Participants’ names are not disclosed to the mixer and the unblinded information will only be known to the randomizer. Is with knowledge of bag contents will be the designated mixer.

Blinding for Clinical Evaluators

To minimize assessment bias, clinical evaluators (data analysts and physicians) will be trained on how to maintain blinding to treatment as best as possible. “Best as possible” means that blinding will be maintained unless an adverse event occurs that requires unblinding the physician, which is determined by the medical monitor or DSMB. Training includes review of the process of blinding, describing who will be responsible for assigning product for the appropriate group, labels that will be used to identify subjects but not treatment group, and the process that should be followed if an adverse event occurs, triggering review by medical monitor and/or DSMB.

Planned Unblinding

Unblinding of patient information will only occur in the case of adverse event suspected to be related to the investigational product, per the medical monitor and DSMB.

Regulatory authorities and/or the IRB may request the unblinding of data from one or more patients at any time.

Investigational Product Assignment and Infusion Schedule (Staggering)

Each patient will be allocated a unique subject number at screening and will retain this number throughout the study.

The Investigational Product is to be administered to all eligible, enrolled patients in Arm 1.1 and Arm 2.1 by intravenous infusion at a dose of 1×10^8 cells at days 0, 3, 7, and 10. Every effort should be made to adhere to the dosing schedule. However, a scheduled infusion should not be administered if a patient has an ongoing AE that, in the Investigator’s opinion, warrants holding the infusion.

Prior and concomitant conditions

The investigators should document all prior significant medical history. Additional conditions present at the time when informed consent is given and up to the time of first infusion (Day 0) are to be regarded as concomitant conditions. Illnesses first occurring or detected during the study and/or worsening of a concomitant condition during the study should be documented as AEs in the CRF. The exception is that results from COVID-19 testing will be added to the CRF as part of medical history.

Prior and concomitant medications

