All SAEs must be reported to Hope Biosciences Stem Cell Research Foundation immediately after the Investigator becomes aware of the event, along with a determination as to whether it is associated with the study drug.

Patients will be instructed to report AEs at each study visit. All AEs are to be followed until resolution or until a stable clinical endpoint is reached.

Each AE is to be documented in the CRF with reference to onset date, duration, frequency, severity, relationship to study drug, treatment of event, and outcome. Furthermore, each AE is to be classified as being serious or non-serious. Changes in AEs and resolution dates are to be documented in the CRF.

For the purposes of this study, the period of observation for collection of AEs extends from the time the patient gives informed consent through day 28 (or early discontinuation visit). Follow-up of the AE is required until the event resolves or stabilizes at a level acceptable to the Investigator.

Intensity of Adverse Event

The intensity of the AE will be judged based on the following:

- Mild: Awareness of sign(s) or symptom(s) which is/are easily tolerated
- Moderate: Enough discomfort to cause interference with usual activity
- Severe: Incapacitating or causing inability to work or to perform usual activities

Causal Relationship of Adverse Events

Medical judgement will be used to determine the relationship, considering all relevant factors, including pattern of reaction, temporal relationship, de-challenge and confounding factors such as concomitant medication, concomitant disease and relevant history. Assessment of causal relationship will be recorded in the CRF.

- **Definitely Related:** The adverse event is clearly related to the investigational product – i.e. an event that follows a reasonable temporal sequence from administration of the study intervention, follows a known or expected response pattern to the suspected intervention, that is confirmed by improvement on stopping and reappearance of the event on repeated exposure and that could not be reasonably explained by the known characteristics of the subject's clinical state.
- **Possibly Related:** An adverse event that follows a reasonable temporal sequence from administration of the study intervention follows a known or expected response pattern to the suspected intervention, but that could readily have been produced by a number of other factors.

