- **Not Related:** The adverse event is clearly not related to the investigational product. - i.e. another cause of the event is most plausible; and/or a clinically plausible temporal sequence is inconsistent with the onset of the event and the study intervention and/or a causal relationship is considered biologically implausible.

Investigator Reporting: Notifying the Study Sponsor

Any study-related unanticipated problem posing risk to subjects or others, and any type of serious adverse event, will be reported to Hope Biosciences Stem Cell Research Foundation (Sponsor) by telephone within 24 hours of the event. To report such events, a Serious Adverse Event (SAE) form will be completed by the investigator and electronically faxed to the sponsor within 24 hours to [contact]. The investigator will keep a copy of this SAE form on file at the study site.

Within the following 48 hours, the investigator will provide further information on the Serious Adverse Event or unanticipated problem in the form of a written narrative. This should include a copy of the completed Serious Adverse Event form, and any other diagnostic information that will assist the understanding of the event. Significant new information on ongoing Serious Adverse Events should be provided promptly to Hope Biosciences Stem Cell Research Foundation.

Routine Study Close-out

The study will end when Hope Biosciences Stem Cell Research Foundation has obtained all data necessary to complete its studies of the investigational product. Standard procedures may include, but is not limited to, review of regulatory documents, collection of completed case report forms, reconciliation of study records, removal or destruction of ancillary study supplies,

and informing the Investigator of remaining obligations (e.g., record retention, final report submission to the IRB, financial disclosure updates, etc.).

Infusion Stopping Rules

Infusion will be stopped when:

- Allergic reaction is aroused after the product has been administered intravenously.
- Patient verbally decline the treatment at any moment prior, or during the infusion.
- Hyperpyrexia develops after infusion administration begins (core body temperature greater than or equal to 40°C) [59].
- PI may stop the study at any time, based upon PI's discretion
- Systolic blood pressure (sbp) ≥ 170 or diastolic blood pressure (dbp) ≥ 90 and sbp ≤ 90 or dbp ≤ 60
- Sudden Severe Hypotension (30-40 mm/Hg drop from pre-infusion level)

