- Elevation or decrease in pulse of 20 bpm or more from baseline
- Change from baseline respiration rate in non-ventilated subjects

Study Alteration Rules

If any of the following events listed below occur, administration of the study drug will be immediately suspended. The Internal Monitoring Committee (IMC), presided by the Medical Monitor will meet to review the incident and its etiology. The committee determine if it is likely related to the drug, the infusion or unrelated. If the IMC along with the Medical Monitor agree that the SAE is unlikely or unrelated to the drug, the study will be continued. If the SAE appears to be definitely drug-related, the study will be stopped. If the SAE is probably or possibly linked to the drug, the IMC will determine the risk to future patients and decide if the study should proceed or be stopped.

Study Stopping Rules

The stopping rules listed below will trigger cessation of enrollment and potential study closure pending a comprehensive DSMB safety review.

1. Any infusion related death, deemed by PI to be associated or possibly associated with study drug.
2. Three or more of the same Grade 3 or higher AEs (judged by the investigator, medical monitor or sponsor), including infusion site reactions.
3. Any event which, in the opinion of the investigator, medical monitor or sponsor, contraindicates further dosing of additional subjects.
4. An infusion related, sustained (over 1 minute) episode of hypoxia (SaO₂ of less than 80%).
5. Any Grade 4-5 Adverse Event as defined in the NCI CTCAE v4.0 and determined to be temporally related to the HB-adMSC infusion by the Medical Safety Monitor and/or DSMB.

After such review, resumption of dosing may be considered, including consideration for any prophylactic interventions (e.g. antihistamines or corticosteroids for injection site reactions).

Medical Monitoring

Medical Monitor

It is the responsibility of the Principal Investigator to oversee the safety of the study at his/her site. This safety monitoring will include careful assessment and appropriate reporting of adverse events as noted above. At Hope Biosciences Stem Cell Research Foundation, [name], MD [contact] will be responsible for reviewing any reported AEs and SAEs to determine if changes to the study need to be made or if the study should be stopped for the protection of patients.

Data Safety Monitoring Board

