- Hands must be washed with soap and water for at least 20 seconds, if soap and running water are unavailable, an alcohol-based hand rub with at least 60% alcohol will suffice this action. Always wash hands that are visibly soiled.
- Avoid touching their eyes, nose or mouth.
- Healthcare workers will wear:
 - o Disposable Gowns
 - o Gloves
 - o Disposable N95 masks.
 - o Eye/face protection (e.g., goggles, face shield)
- Surfaces where subjects have been in contact will be disinfected 70% Isopropyl Alcohol.

Pre-infusion Medication

Prior to infusion, medications will be given to the participant as a precaution. Because the drug for this study is an allogeneic product, an allergy medication such as Loratadine (10mg), will be administered. The participant will be closely monitored for any signs of allergic reaction during the infusion and during the post-infusion monitoring period. No reactions are expected.

Potential Benefits

Subjects may benefit from their participation in the study by experiencing an overall feeling of well-being. Subjects enrolled in the study will be contributing to the advancement of science and to future investigations regarding stem cells and possible therapeutic applications, including treatment of respiratory diseases, specifically COVID-19.

Statistical Analysis

Determination of Sample Size

Sample size calculation was determined based upon the anticipated demand for treatment.

Null hypothesis- Efficacy

Treatment with HB-adMSCs does not cause changes in primary and secondary endpoints (listed below) for suspected Corona Virus Disease.

Alternative hypothesis-Efficacy

The alternative hypothesis for this study is that HB-adMSC treatment does result in changes from baseline values of primary and secondary endpoints in patients with suspected Corona Virus Disease.

Null hypothesis-Safety

Treatment with HB-adMSCs results in adverse or serious adverse events and/or detrimental changes in laboratory values, vital signs, weight, X-rays, EKG, or physical examination determined to be related to the study drug.

Alternative hypothesis-Safety

HB-adMSC treatment for COVID-19 does not result in adverse or serious adverse events and/or detrimental changes in laboratory values, vital signs, weight, X-rays, EKG, or physical examination determined to be related to the study drug.

Endpoints

The endpoints measured in this study are safety and clinical efficacy.

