#### **7.2.4.2. Data Analytic Models**

All secondary endpoint efficacy measurements available at post-baseline at scheduled measurements (Visits 2 through 5 [infusions 1 through 4] for exploratory markers and clinical labs; Visits 2 through 6 [infusion 1 through end of treatment] for chest X ray, CT scan, and ordinal scale score) will be analysed in a generalized linear mixed model. The model will predict each outcome as a function of the interaction between the fixed factors treatment group and time, controlling for lower order effects of time and treatment group. Models will control for stratification variables (see [Covariates and Other Strata](#)), and subject will be included as random effects. AEs/SAEs and AE severity will be analyzed as dichotomous outcomes (whether patient exhibited AE/SAE at any time during the study). AE/SAE attribution to study drug will be analyzed as count outcomes. All models will control for stratification variables.

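### The three adverse-event causality levels are not exhaustive: an unexpected, plausibly timed reaction with no better explanation fits none of them

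*Protocol*

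**What the plan says.** The protocol section Causal Relationship of Adverse Events defines three levels and asks for the assessment to be entered in the CRF for each AE.

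- **Definitely Related** needs reasonable timing, a recognised response pattern "that is confirmed by improvement on stopping and reappearance of the event on repeated exposure", and no reasonable explanation in the patient's clinical state.
- **Possibly Related** needs the event to be one that "follows a known or expected response pattern to the suspected intervention, but that could readily have been produced by a number of other factors", with reasonable timing.
- **Not Related** is for an event clearly unrelated to the product, because "another cause of the event is most plausible", or the timing does not fit, or a causal link is biologically implausible.

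A sentence before the definitions calls for medical judgement, weighing pattern, timing, dechallenge and confounders.

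The result is analysed. SAP 7.2.4.2 states that "AE/SAE attribution to study drug will be analyzed as count outcomes", and SAP 8.1 plans AE summaries by relation to treatment.

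**The concern.** A causality scale has to give every event a place. This one makes expectedness an entry condition for both related levels, although expectedness is a separate question from causation. It also makes rechallenge a condition of the top level, although many events cannot be rechallenged. A Phase II study of an allogeneic cell product needs to be able to record a reaction that nobody anticipated. As worded, the scale has no correct box for one.

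Two assessors facing the same unplaceable event can choose different levels, and neither will be following the definitions. Genuine reactions to the product can occur only in patients given HB-adMSCs, so any that are entered as Not Related are lost from that arm's related-event count. Safety is part of the primary objective, so the attribution results will be read.

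**Working it through.** No arithmetic applies, and the plan gives no figure to reproduce. The check sets out the conditions for each level and runs cases through them. 'Recognised pattern' below stands for the protocol's expectedness condition.

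| Condition | Definitely | Possibly | Not Related |
|---|---|---|---|
| Plausible timing | required | required | inconsistent timing is one way in |
| Recognised pattern | required | required | not mentioned |
| Improvement on stopping | required | not mentioned | not mentioned |
| Recurrence on re-exposure | required | not mentioned | not mentioned |
| Other causes | must not reasonably explain it | must readily be able to explain it | a more plausible cause is one way in |
| Biological implausibility | not mentioned | not mentioned | one way in |

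**Case 1. Unexpected pattern, plausible timing, no better explanation.** It fails Definitely and Possibly on the recognised-pattern condition. It fails Not Related because no other cause is more plausible, the timing fits and the link is not implausible. It has no level.

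**Case 2. Recognised pattern, plausible timing, no competing cause, no re-exposure.** It fails Definitely because recurrence has not been shown. It fails Possibly because no other factors could readily have produced it. It fails Not Related for the same reasons as Case 1. It has no level.

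**Case 3. Death as the event itself.** A death cannot improve on stopping or recur, so Definitely is closed. With a recognised pattern and other factors that could readily explain it, Possibly is the highest level open. With a recognised pattern and no competing cause it falls into Case 2. With a new pattern and no better explanation it falls into Case 1.

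**Case 4. Recognised reaction that resolves, recurs at a later infusion and has no other reasonable explanation.** It meets Definitely, so that level is not empty.

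**How often re-exposure is available.** Infusions are planned on Days 0, 3, 7 and 10. A reaction to one of the first three could recur at a later one. A reaction that first appears after the Day 10 infusion has no later infusion at which to recur. A severe allergic reaction is a listed ground for discontinuing treatment (Withdrawal, Removal, and Replacement of Patients), which removes the chance to observe recurrence.

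**Which outputs use the classification.**

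| Output | Depends on the causality level? |
|---|---|
| Attribution counts (SAP 7.2.4.2) | yes |
| AE summaries by relation to treatment (SAP 8.1) | yes |
| Any AE or SAE during the study, analysed yes/no (SAP 7.2.4.2) | no |
| Treatment-emergent status (SAP 8.1) | no, defined by timing |
| SAE reporting to the sponsor (Protocol, Investigator Reporting) | no, covers every SAE |
| Study Stopping Rules | no (see the objection) |

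**The case against.** **Medical judgement.** The lead-in sentence lets an assessor weigh all factors, so a sensible investigator would record an unexpected reaction as Possibly Related. That may happen in practice. But the definitions turn pattern and dechallenge from factors to weigh into conditions to meet, and no exception is given. The lead-in and the definitions pull apart, which is why the outcome is arbitrary.

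**The scale drives the study stop and unblinding.** A reader might infer this from the Study Alteration Rules ("If the SAE appears to be definitely drug-related, the study will be stopped") and from Planned Unblinding ("Unblinding of patient information will only occur in the case of adverse event suspected to be related to the investigational product"). The documents do not support it. The Internal Monitoring Committee reviews the incident and reaches its own view, in terms that differ from the three levels. It may also stop the study for a lesser link. Unblinding is decided by the medical monitor and DSMB. Neither passage cites the causality definitions.

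**Fatal or novel reactions escape safety action.** This does not follow either. Stopping Rule 1 needs no more than a possible association with the drug. Rule 2 counts repeated Grade 3 or higher events without a causality test. Rule 3 rests on the opinion of the investigator, medical monitor or sponsor. Rule 5 rests on temporal relation. The DSMB reviews all deaths.

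**Almost nothing counts as expected.** Under Pre-infusion Medication the protocol says "No reactions are expected", which might suggest that even allergy lies outside the recognised patterns. The sentence follows premedication and monitoring for allergy, and anaphylaxis has its own appendix. The protocol also names thromboembolic, hepatic and coagulation risks, and lists infusion-related reactions, serious infections, hepatotoxicity, heart failure and cytopenias as safety endpoints. The consent form, which is not available here, may add others. The recognised set is of reasonable size, so the gap concerns reactions outside it, together with Case 2.

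**Confirmed reactions only.** Keeping the top level for rechallenge-confirmed events is partly a matter of preference. That is fair, but it then requires a lower level able to take the rest, and Possibly Related as defined cannot.

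**Conclusion.** The point holds as a defect of wording: the three definitions do not cover all AEs. Unexpected reactions without a better explanation have no level. Nor do recognised reactions with neither a competing cause nor re-exposure. A death as the event itself cannot be Definitely Related. The one arguable exception to that last statement is a recognised reaction that resolved after one infusion and recurred fatally after a later one.

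The exposure is limited to the per-AE relationship record and the two SAP outputs built on it. No number of affected events can be given, because the documents state no rate for such reactions.

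Under-counting is a possibility, not a demonstrated bias. A reader might infer that the form forces these events into Not Related, but the CRF is not among the documents, and by its own terms Not Related does not fit them. The conclusion rests on reading the listed conditions of each level as jointly required, which is how they are written.

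**What to change.** - Reword the three definitions so that every AE fits exactly one level. Remove the recognised-pattern requirement from both related levels and record expectedness in a separate CRF field. Treat dechallenge and re-exposure as supporting evidence where available.
- Refer to the revised levels in SAP 7.2.4.2 and 8.1. The SAP is marked as a draft, so this is still open.
- Re-assess AEs already recorded against the new definitions, by blinded assessors, where blinding is intact.
- Separately, reconcile the terms in the Study Alteration Rules with the scale. *Probably* and *unlikely* appear there but are not levels. No stopping action needs to change for this.

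The cost is protocol and CRF wording, a short notice to the sites, and the time for blinded re-assessment.

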Patients will receive four intravenous infusions of 100 million HB-adMSCs throughout the entire duration of the study.

Arm 2 (placebo) (n=40)

Patients will receive four intravenous infusions of placebo (saline solution) throughout the entire duration of the study.

Safety assessments will be ongoing. Safety tests will include EKG, Complete Blood Count with differential, Complete Metabolic Profile (to include renal function and hepatic function) and Coagulation Panel screening for hepatotoxicity, cytopenias, renal failure or alterations in the coagulation cascade that might entail a safety concern for the individual. Efficacy will be measured by change from baseline in inflammatory markers (IL-6, CRP, IL-10, TNF-alpha), change from baseline in oxygenation, and time to receive negative PCR test result, change from baseline in exploratory markers (D-dimer, myoglobin, troponin, creatinine kinase, serum ferritin, CD3CD56, CD4/CD8, VEGF), time to return to room air (RTRA), change from baseline chest x-ray, change from baseline CT scan, and change from baseline in 7-point ordinal scale.

Selection and Withdrawal of Patients

Inclusion Criteria

1. Men, and women, over 18 years of age inclusively.
2. Suspected COVID-19 infection
3. Provides consent or consent is given by their legally authorized representative (LAR)
4. Agrees to the collection of venous blood per protocol.

Exclusion Criteria:

1. Pregnancy, lactation and those who are not pregnant but do not take effective contraceptive measures, in women of childbearing age.
2. Patients who have participated or are participating in a clinical trial of an experimental vaccine for SARS-CoV-2 or coronavirus during the study or within 30 days.
3. Inability to provide informed consent or to comply with test requirements.

4. Any medical disease or condition that, in the opinion of the site Principal Investigator or sub-investigator, precludes study participation. Including acute, subacute, intermittent or chronic medical disease or condition that would place the subject at an unacceptable risk of injury, render the subject unable to meet the requirements of the protocol, or may interfere with the evaluation of responses or the subject's successful completion of this trial.

Withdrawal, Removal, and Replacement of Patients

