Patients will be considered to have completed the study if they complete treatment and assessments through day 28. A patient's investigational treatment should be discontinued if any of the following situations occurs:

- The Investigator believes that for safety reasons, it is in the best interest of the patient to stop treatment.
- The patient is non-compliant with the study visit schedule or other protocol requirements.
- The patient develops a severe allergic reaction that occurs following investigational product administration.

A patient may voluntarily withdraw or be withdrawn from the study at any time for reasons including, but not limited to, the following:

- Patient withdrawal of consent: At any time, a patient's participation in the study may terminate at his/her request. The specific reason for patient withdrawal will be noted on the case report form (CRF).
- Lost to follow-up: The patient stops coming for visits, and study personnel is unable to contact the patient after repeated attempts (e.g., mail, or email).
- This study may be terminated at the discretion of the Sponsor or any regulatory agency.

If a patient's infusions are discontinued at any point during the trial and the patient maintains consent to contribute additional outcome information, the patient should continue to be followed through day 28 for all safety and efficacy assessments. Investigators will be trained about the importance of retention and steps to prevent missing data. The date and reason for withdrawal are to be documented in the CRF. The study site(s) must immediately notify the medical monitor. The patients who withdraw prematurely must attend an early discontinuation visit if possible, at which time they will complete all assessments described in Table 2 under day 28. Unless the patient declines (consent withdrawn), the follow up phone call at day 28 should be done in all patients who were enrolled in the study regardless of their enrollment status.

In the event that a patient discontinues prematurely from the study due to an Adverse Event (AE) or serious AE, the event will be followed until it resolves (returns to normal or baseline values) or stabilizes, or until it is judged by the Investigator to be no longer clinically significant. Once a patient is withdrawn from the study, the patient may not re-enter the study.

Treatments

Details of the investigational product

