Allogeneic HB-adMSCs, from a single qualified donor, is to be administered as an IV infusion. Each syringe will be provided by Hope Biosciences on the day of the infusion after all quality control essays have been performed and the results are within normal range.

Instructions for Administration

The designated study staff will administer the investigational product in the following manner:

- Prior to administration, visually inspect the infusion solution for particulates. If foreign particles are present, do not use the solution.
- Emergency equipment, such as epinephrine, antihistamines, and corticosteroids must be available in the event of infusion-related reactions.
- Start IV administration after dilution.
- Administer the infusion solution over a period of 1h. Observe the patient for at least 1-hour post-infusion for acute infusion-related reactions, including anaphylaxis. Continual monitoring will resume, with hospital staff observing vital signs, including blood pressure, pulse, or signs of rash/hives. Acute increase or decrease (30-40 mm/Hg from pre-infusion level) in blood pressure, an elevation of more than 20 BPM from baseline, or appearance of rash/hives would warrant review by PI.
- See Appendix 1 for guidelines on diagnosing anaphylaxis.
- Do not store or reuse any unused portion of the infusion solution. Any unused product or waste material should be disposed.
- Volume of study drug infused, start times, and stop times will be recorded. If any portion of the infusion (cell solution) is discarded, the reason will be recorded in the CRF.
- The patient will be monitored for a total of 2 hours from drug exposure to discharge.
 - a. During the Investigational product administration (1 hour) vital signs will be measured at minute 0, 15, 30 and 45.
 - b. Post infusion, vital signs will be measured at minute 0, 30, and 60.

Investigational Product Assignment (Randomization and Blinding)

Randomization

A total of 100 eligible subjects will be randomized to either placebo or treatment group within the associated study arm at baseline. Randomization will determine whether the subject receives placebo or HB-adMSCs.

A neutral, third-party personnel will be responsible for assigning the participants' treatment group. This role will be referred to as 'randomizer'. The designated personnel from the drug manufacturer will be responsible in labeling and packaging the investigational product for each

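### The blood pressure infusion-stopping bullet joins its high and low limits with 'and'; read literally it never stops an infusion for an isolated dbp ≥90 or an isolated sbp ≤90, most likely a slip for 'or'

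*Protocol*

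**What the plan says.** In the protocol, Infusion Stopping Rules is a list of conditions, each of which requires the infusion to be stopped. The only bullet with absolute blood pressure limits reads "Systolic blood pressure (sbp) ≥ 170 or diastolic blood pressure (dbp) ≥ 90 and sbp ≤ 90 or dbp ≤ 60".

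The other bullets that bear on the same patients are:

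- an allergic reaction after the product is given;
- a relative fall in pressure, "Sudden Severe Hypotension (30-40 mm/Hg drop from pre-infusion level";
- a pulse that moves by at least 20 bpm in either direction;
- a respiration trigger, "Change from baseline respiration rate in non-ventilated subjects", with no minimum size;
- a discretion clause, "PI may stop the study at any time", which is worded as stopping the study.

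Elsewhere in the protocol, Instructions for Administration sends an "Acute increase or decrease (30-40 mm/Hg from pre-infusion level) in blood pressure" to the principal investigator for review. That prompts a review, not an automatic stop. The same section has vital signs taken at minutes 0, 15, 30 and 45 of each infusion. Withdrawal, Removal, and Replacement of Patients ends treatment if "The Investigator believes that for safety reasons, it is in the best interest of the patient to stop treatment". The entry criteria set no blood pressure limit, apart from excluding "Any medical disease or condition that, in the opinion of the site Principal Investigator or sub-investigator, precludes study participation".

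Neither the protocol nor the SAP states the four limits a second time.

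**The concern.** The bullet is a mandatory numeric threshold. It is checked repeatedly during each of four infusions, at two sites. With *and* between the high and low pairs, the sentence as written describes a rule under which two of its four limits never act alone. A reader who applies it literally would let an infusion continue at 160/100 or at 85/65.

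What is at stake is whether both sites apply the same threshold without having to infer it. The gap matters most for dbp ≥90. An enrolled patient may have a stable diastolic pressure at that level, and a stable reading triggers none of the change-based rules.

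**Working it through.** **Inputs** (all from the stopping bullet). Let A be sbp ≥170, B be dbp ≥90, C be sbp ≤90 and D be dbp ≤60. The text is A or B and C or D, with no brackets. There are five ways to bracket it. Two of them, (A or (B and C)) or D and A or ((B and C) or D), are the same rule, so four distinct literal rules remain.

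**Two readings by hand**

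- 160/100: only B is true.
- 85/65: only C is true.

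In every bracketing, B is and-ed with a term built only from C or from C and D, and C is and-ed with a term built only from B or from A and B. If B alone is true, the other side of the *and* is false. If C alone is true, the same holds. Neither reading can stop the infusion.

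**Results by rule**

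| Rule | 160/100 | 85/65 | 180/100 | 85/50 | 175/55 |
|---|---|---|---|---|---|
| A or (B and C) or D | no | no | stop | stop | stop |
| (A or B) and (C or D) | no | no | no | no | stop |
| ((A or B) and C) or D | no | no | no | stop | stop |
| A or (B and (C or D)) | no | no | stop | no | stop |
| A or B or C or D | stop | stop | stop | stop | stop |

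Under the usual precedence (first row), the middle term needs dbp ≥90 together with sbp ≤90. That cannot occur, because systolic exceeds diastolic. The rule then reduces to sbp ≥170 or dbp ≤60. Under the paired grouping (second row) it fires only when sbp ≥170 and dbp ≤60 together.

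**Exhaustive check.** All integer pairs with sbp 60-230, dbp 30-130 and sbp > dbp were run through each rule.

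- Isolated dbp ≥90 (sbp 91-169): the count is (1 + 2 + … + 41) for sbp 91-131, plus 38 × 41 for sbp 132-169, so 861 + 1558 = 2419 pairs. Each of the four literal rules stops 0 of 2419; four *or*-joined limits stop 2419 of 2419.
- Isolated sbp ≤90 (dbp 61-89): the count is 1 + 2 + … + 29 = 435 pairs. Each literal rule stops 0 of 435; four *or*-joined limits stop 435 of 435.

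These are counts of possible readings, not of patients. The documents give no blood pressure distribution, so no frequency can be stated.

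**Do the neighbouring rules fill the gap?** Two illustrative changes, with pre-infusion values assumed:

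- 140/85 to 160/100 is a rise of 20/15 mmHg, below the 30 mmHg that prompts review. The drop bullet does not apply to a rise.
- 110/70 to 85/65 is a fall of 25/5 mmHg, below the 30 mmHg at which the drop bullet starts.

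Either patient could still be stopped by the pulse, respiration or allergic-reaction bullet if those signs were present, or by investigator judgement. None of these turns on the absolute pressure.

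**The case against.** The strongest answer is that nobody would apply the literal rule. In a list of stopping conditions, high limits *and* low limits is ordinary English for two out-of-range bands. The literal readings also defeat themselves: one contains a combination that cannot occur, and another lets both 180/100 and 85/50 continue. That stands, and it is why this is a drafting slip and not a design decision. A reader might infer that the sponsor chose to ignore isolated diastolic hypertension, or that infusions were run through unsafe pressures. Nothing in the documents supports either.

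The second answer is that the backstops are substantial on the low side. A patient becoming hypotensive may well meet the pulse bullet or the respiration bullet, which has no minimum size. Appendix 1 counts reduced blood pressure towards anaphylaxis under criterion 1 (with skin or mucosal signs), criterion 2 (with another feature after a likely allergen) and criterion 3 (after a known allergen), and allergic reaction is itself a stopping bullet. This also stands. It narrows the gap without closing it, because these routes need other signs or a known allergen, and the respiration bullet leaves out ventilated patients.

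It is also tempting to size the low-side gap by saying that a systolic reading of 85 escapes the drop bullet for every pre-infusion systolic pressure up to 85 + 29 = 114. That assumes the drop bullet means systolic pressure, which it does not say. A change from 114/95 to 85/65 is a diastolic fall of 30 mmHg and could meet it. The claim for every such patient should not be made.

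**Conclusion.** The point holds as a minor wording error in a mandatory safety rule. Read literally, under every possible bracketing, the bullet does not stop an infusion for sbp 91-169 with dbp ≥90, or for sbp ≤90 with dbp 61-89. Under the evident intent it stops all of them. The literal result rests only on the bullet's wording and on systolic exceeding diastolic. The view that it is a slip is a judgement, though a safe one.

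Other bullets and investigator discretion cover part of the gap, more on the low side than the high side. None supplies an absolute limit at dbp ≥90 or sbp ≤90.

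There is no effect on sample size, power or alpha. A reader might infer an effect on the efficacy results, since the efficacy set requires all four infusions. The documents do not show one: they do not say how sites read the bullet, or whether a stopped infusion counts as received.

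**What to change.** Reword the bullet to: sbp ≥170 or dbp ≥90, or sbp ≤90 or dbp ≤60. The cost is a small text change in an amendment and a short note to the two sites, with no added assessments or observation time.

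The downside is small but should be known. With each limit acting alone, an infusion continues only at sbp 91-169 with dbp 61-89, so a patient whose stable pre-infusion diastolic pressure is already ≥90 or ≤60 is at a stopping limit from minute 0. Whether the thresholds suit such patients is a separate clinical question for the medical monitor, and the wording correction need not wait for it.

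The SAP is a draft dated 7 November 2022, so dosing may already be over; the documents do not say. If it is, a sentence in the study report on how the sites applied the four limits would serve instead.
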